9. RESEARCH DESIGN AND METHODS

This will be a single-center (UCSD), randomized, participant- and observer-masked, sham-controlled, parallel-arm human subjects pilot study.

Enrollment. Participants will be consenting adults either (1) undergoing various surgical procedures usually resulting in moderate-to-severe postoperative pain, or (2) experience post-amputation phantom and/or residual limb pain. Study inclusion will be proposed (1) to eligible presurgical patients or (2) after an amputee contacts the investigators. If an individual desires study participation, written, informed consent will be obtained using a current UCSD IRB-approved ICF. The study population of interest includes adult women and men of all races, ethnicity, sexual identity, and socioeconomic status. Inclusion and exclusion criteria are listed in section #10 below.

Procedures. Following written, informed consent, we will record baseline anthropometric information (age, sex, height, weight, amputation details and current pain levels). Surgical participants will receive any standard peripheral nerve block(s) administered using bupivacaine or ropivacaine 0.5% with epinephrine (standard at UCSD) prior to undergoing their surgical procedure *per standard of care*.

Treatment Group Assignment. Each participant will be randomized to one of two treatment groups: *Active* or *Sham* treatment. For the initial 150 subjects of Phase I, there are sham RecoveryRx devices produced that are identical to active RecoveryRx devices, only they do not deliver PEMF. Randomization will be stratified by surgical procedure/amputation, in block sizes of 2. The computer-generated randomization lists will be created by the University of California San Diego Investigational Drug Service in a 1:1 treatment group ratio using opaque envelopes. For the initial 150 subjects of Phase I using RecoveryRx devices, the active and sham devices are indistinguishable in appearance, and therefore investigators, participants, and all clinical staff other than the individual who opens the randomization envelope and chooses a sham or active device will be masked to treatment group assignment for the duration of the data collection period. For the subsequent 80

subjects of Phase II, active SofPulse devices will be provided to patients randomized to the active treatment group; and sham RecoveryRx devices will be provided to the patients randomized to the sham treatment group.

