Study intervention. For surgical patients of Phase I, the PEMF device (2 devices, if there are multiple incisions or the incision is larger than the device diameter; 3 devices for total knee and hip arthroplasty or spinal surgery) will be affixed over the primary wound area(s) using tape and activated prior to recovery room discharge (*Experimental*). For surgical patients of Phase II, a single PEMF device will be used for each participant due to their larger diameter and treatment area. For amputees, the device used is over-the-counter (ActiPatch, BioElectronics, Frederick, Maryland) and 2 devices (both the same treatment group) will be shipped to the patient either in or out of California who will then contact an investigator for assistance in self-placement of the device on the residual limb. The optimal location to treat phantom pain is currently unknown and will partially informed by the results of this pilot study, and patients will be encouraged to move the devices to a new anatomic location every two days until relief is experienced.

Supplemental analgesics. In addition to the PEMF device(s), participants will receive standard-ofcare supplemental analgesics which can include acetaminophen, ibuprofen, ketorolac, opioids, gabapentin (this is provider- and patient-dependent). *Therefore, all patients of this study—regardless* of the treatment arm they are randomized to—will continue to receive current usual and customary analgesia: all will receive the same combination of supplemental analgesics they would regardless of study participation (of note, amputees will be asked to continue their normal analgesic regimen, including any as-needed treatments). Participants (and their caretakers of surgical patients) will be provided with verbal and written instructions, and the telephone and pager numbers of an investigator available during business hours throughout the treatment period. Participants can shower with the device in place, but not submerge it during swimming or a bath, as advised by the manufacturer.

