Surgical participants will be discharged with their PEMF device(s) *in situ* and a prescription for immediate-release oral opioid, preferably oxycodone 5 mg tablets, taken for breakthrough pain (surgeons occasionally prefer a different type of opioids such as hydrocodone, which is why we analyze the data using oral oxycodone equivalents). The PEMF devices will be removed by participants at home following Day 8 (SofPulse) or Day 30 (Actipatch/RecoveryRx) when the battery is exhausted (participants may remove them as early as Day 7, if they desire). Removing the devices encompasses tape removal and discarding in the trash (these are disposable, single-use devices).

Amputees will return their initial devices in pre-addressed and -stamped envelopes that we provide. They will be sent a second device which is the opposite treatment of the initial device: participants who initially received sham will subsequently receive active, and vice versa. These will be applied on Day 35 and the same protocol will be repeated as for the initial device, with additional data collected for 35 days after placement of the second device. The second device will be discarded in the trash.

Of note, if a device is reported lost or nonfunctional during the study, it will be replaced by the investigators by mail if more than 7 days of treatment remain.

Outcome measurements (end points). We have selected outcome measures that have established reliability and validity, with minimal inter-rater discordance, and are recommended for pain-related clinical trials by the Initiative on Methods, Measurement, and Pain Assessment in

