Clinical Trials (IMMPACT) consensus statement. All data collection will be through standard UCSD EPIC notes and patient interviews in-person during hospitalization or *via* a telephone call for outpatients. Postoperatively, surgical endpoints will be recorded such as surgical duration. All pain scores will be measured using the Numeric Rating Scale (0: no pain, 10: worst imaginable pain). On Days 35 and 70, amputees will be asked if they would want to continue using the device; and on Day 28 surgical patients will be asked if they would want to use the device if they were to have the same surgery in the future? For Phase II surgical participants, Days 21 and 28 will be excluded due to the shorter treatment period (8 days) of this device relative to that used in Phase I. At all time points for amputees, phantom and residual limb pain will be distinguished and recorded separately.

	Surgical Patients Postoperative Days								Amputees Post-Application Days						
Time Point:															
	1	2	3	7	14	21	28	180	0	2	4	7	21	28	35
Opioid consumption	•	•	•	•	•	•	•	•	•	•	•	•	•	•	•
Average Pain [NRS]	•	•	•	•	•	•	•	•	•	•	•	•	•	•	•
Worst Pain [NRS]	•	•	•	•	•	•	•	•	•	•	•	•	•	•	•
Brief Pain Inventory,				_	_	-	•							•	
Short Form				•	•	•	•		•					•	•
Patient Global												_	•	•	
Impression Change										•	•	•	•	•	•
Sleep disturbances	•	•	•		•	•	•		•	•	•			•	
(#) previous night	•				-					-	-				-
Passive flexion					•										
(knees and hips)															

Summary of post-enrollment assessments (color added for clarity)

Primary end points: This is an exploratory pilot study to assist in planning subsequent definitive trials and we therefore have no data analysis plan. For surgical patients, the two outcomes of primary interest will be (1) the "average" and "worst" pain measured with the Numeric Rating Scale (included in the Brief Pain Inventory pain domain), and (2) opioid consumption within the first 7 postoperative days. For amputees, the outcome measures of primary interest will be (1) the change in "average" residual and phantom limb pain scores between baseline and Day 28 of the initial treatment, as well as (2) the Patient Global Impression of Change on Day 28 of the initial treatment.

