For Phase II, there will be a total of 70 surgical participants, and these patients will be analyzed separately from Phase I surgical and amputation patients. Sample size calculations are based upon the hypothesis that pulsed electromagnetic field therapy decreases **pain** in the 7 days following moderate-to-severely painful surgical procedures. The primary outcome calculated as follows: for each participant all of the "average" and "worst" daily pain scores collected within the first 7 postoperative days will be summed. We will use these summed scores from participants having cholecystectomy (n=30), and hip and knee arthroplasty (n=40) to estimate a probable sample size.

We will consider a 33% reduction in pain scores to be the minimal clinically important difference [Farrar et al. J Pain Symptom Management 2003; 25: 406-11]. Based on values from patients receiving sham in Phase I, we anticipate the sham group to have an anticipated mean (SD) of 23.9 (12.3). Assuming a two-sided type I error protection of 0.05 and a power of 0.80, approximately 25 patients in each group are required (ClinCalc.com, accessed 2/23/23). To allow for a higher degree of variability than anticipated we will enroll a total of 70 participants in Phase II: cholecystectomy (n=30), and hip and knee arthroplasty (n=40).

Continuous, normally-distributed data will be reported as mean ± standard deviation. Nonparametric continuous or categorical data will be reported as median [10th-90th percentiles] or precents, as appropriate. Comparisons of independent samples will be performed using Student's t-test for parametric continuous variables or Mann-Whitney U test for nonparametric or categorical variables. The Chi Square test and Fisher's Exact test will be used for differences in proportions, as appropriate. P<0.05 will be considered statistically significant for the primary outcome. Results of comparisons in secondary outcomes will be interpreted as suggestive, requiring confirmation in a future trial before considering them as definitive.

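### As written, the rule for replacing a lost or failed device in Phase II runs for about 1 day in the active arm and about 23 days in the sham arm

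*Combined protocol and SAP*

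**What the plan says.** All the relevant text is in section 9 of the combined protocol and SAP.

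- **Replacement.** In the paragraphs just before the outcome measurements, the plan says of a device reported lost or nonfunctional that "it will be replaced by the investigators by mail if more than 7 days of treatment remain". The sentence covers the whole study and makes no distinction by phase, arm or product.
- **Removal.** Slightly earlier, surgical participants are to take the device off "following Day 8 (SofPulse) or Day 30 (Actipatch/RecoveryRx) when the battery is exhausted", with the option that "participants may remove them as early as Day 7, if they desire".
- **Phase II devices.** Under Treatment Group Assignment, "active SofPulse devices will be provided to patients randomized to the active treatment group", whereas "sham RecoveryRx devices will be provided to the patients randomized to the sham treatment group".
- **Number of devices.** Under Study intervention, in Phase II "a single PEMF device will be used for each participant due to their larger diameter and treatment area".
- **Treatment period.** Under Outcome measurements, the plan drops two of the later assessments from the Phase II schedule: "Days 21 and 28 will be excluded due to the shorter treatment period (8 days) of this device relative to that used in Phase I".
- **Primary outcome.** For Phase II, the average and worst "daily pain scores collected within the first 7 postoperative days will be summed".

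**The concern.** In Phase I both surgical arms used the same product, so a rule based on remaining treatment time applied to them equally. In Phase II the product, and with it the stated removal day, is fixed by the randomised arm. A threshold of more than 7 days remaining then closes almost at once for the 8-day product and stays open for weeks for the 30-day one.

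Two things are at stake. The first is equal handling after randomisation. For most of the period in which the primary pain scores are collected, two participants who report the same problem on the same day would get different answers because of their arm. Each Phase II participant has one device, so a loss leaves nothing in place. A participant sent a new device may also keep the belief of being treated, which could matter for a self-reported pain score.

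The second is masking. The title and section 9 describe the study as participant- and observer-masked. Whoever applies this rule must first establish which product the caller has, and in Phase II that identifies the arm.

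**Working it through.** The plan states no replacement window for either arm, so there is no figure to reproduce. The check is a subtraction from the plan's own numbers.

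**Inputs** (all from section 9): threshold, more than 7 days of treatment remaining; removal day, 8 for SofPulse and 30 for RecoveryRx; Phase II active arm on SofPulse and sham arm on sham RecoveryRx; primary outcome window, the first 7 postoperative days. The removal days are given by product name, with no separate entry for a sham unit, so the sham RecoveryRx is taken at Day 30.

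**Formula:** days during which a reported loss qualifies = treatment period − 7.

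- Active: 8 − 7 = 1 day. This is 1/8 = 12.5% of the treatment period and 1/7 = 14% of the primary window.
- Sham: 30 − 7 = 23 days. This is 23/30 = 77% of the treatment period and covers the whole primary window.

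The plan does not say how part-days are counted, so the boundaries are approximate.

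| When the loss is reported | Active (SofPulse) | Sham (RecoveryRx) |
|---|---|---|
| Before about Day 1 | eligible | eligible |
| About Day 1 to Day 8 | not eligible | eligible |
| After Day 8, to about Day 23 | treatment period over | eligible |
| After about Day 23 | treatment period over | not eligible |

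**Overlap with the primary outcome.** The assessment table schedules pain scores within the first 7 days on Days 1, 2, 3 and 7. Three of these four days (2, 3 and 7) fall after the active-arm window has closed; all four fall inside the sham-arm window. The part of the sham window after Day 7 has no bearing on the primary outcome.

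**Alternative reading.** If *treatment* means a common 8-day period for everyone in Phase II, the window is 8 − 7 = 1 day in both arms and there is no difference. For the sham arm, then, the same sentence gives 1 day or 23 days depending on an undefined word.

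**The case against.** The strongest reply is that the rule refers to days of treatment, not to battery life, and that section 9 drops the Day 21 and Day 28 assessments for all Phase II surgical participants because of an 8-day treatment period. If that is the treatment period for Phase II as a whole, the arms are treated alike. This reading is open. It is not settled, because the text ties the 8 days to the device, which can only be SofPulse, and uses them only to shorten follow-up. The replacement sentence does not adopt them, and the removal sentence gives RecoveryRx 30 days.

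A reader might also infer that the asymmetry costs power, since active participants whose device is not replaced stay untreated and dilute the effect. The documents do not support that. A replacement sham delivers no PEMF, so the loss in the active arm would be the same if the sham arm were also held to 1 day, and making the rule equal would not by itself recover any power. Any power figure would also need a loss rate, which the plan does not give. It would need an assumption about how much of the effect each loss removes, when scores are taken on only four days. Replacement is by mail, so a device lost late in the week may not be restored before the Day 7 score under any rule.

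A reader might further infer that every such call unmasks the participant. That goes too far. Before about Day 1 both arms qualify, and after about Day 23 neither does. Nothing says participants are told of the 7-day threshold. The plan claims indistinguishable devices only for Phase I, and staff who apply the rule by product already know the product. The rule adds to a masking weakness that Phase II already has.

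Finally, this is a contingency clause in a self-described exploratory pilot, and it may seldom be used. That limits its importance but does not remove the inconsistency.

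**Conclusion.** The point holds as a written inconsistency with a modest consequence. On the literal text, eligibility for replacement in Phase II lasts about 1 day in the active arm and about 23 days in the sham arm. The arms are therefore handled differently from about Day 1 to Day 7, within the primary window, and a caller's answer depends on arm until about Day 23.

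This rests on two assumptions: that *treatment* runs to the removal day stated for each product, and that the Day 30 entry for RecoveryRx applies to its sham version. If the 8-day period governs both arms, the asymmetry is nil and only the wording needs attention.

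The size of any effect on the result cannot be calculated, because the plan gives no loss or failure rate; it is probably small. What remains is differential handling and an arm-dependent reply in a study described as masked.

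**What to change.** Reconcile the statements in section 9 on Phase II device assignment, removal days, the 8-day treatment period and replacement, so that eligibility for replacement in Phase II does not differ by randomised arm. The plan should say what *treatment* means for the Phase II sham arm. Which replacement rule to adopt is for the sponsor to decide.

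Record each reported loss or failure with its day and arm. This also serves Specific Aim 1, on feasibility and protocol optimisation, and would supply the rate that is now missing.

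The cost is one sentence, a log field and possibly a few spare devices. The drawback is that some mailed replacements may arrive too late to help.

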10. HUMAN PARTICIPANTS

We will recruit a convenience sample with a maximum of **270 participants in total (all participants who sign an informed consent included)**. Selection for inclusion will not be based on race, ethnicity, sexual identity, or socioeconomic status. There will be no participants from vulnerable populations, such as pregnant women, children, or prisoners.

Inclusion criteria (amputees): Adult patients of at least 18 years of age [19 years in Alabama and Nebraska], (1) with an upper or lower limb amputation at least 12 weeks prior to enrollment distal to the shoulder or hip (femoral head remaining), respectively, and including at least one metacarpal or metatarsal bone, respectively; (2) who experience at least moderate residual and/or phantom limb pain—defined as a 3 or higher on the Numeric Rating Scale (NRS; 0-10, 0= no pain; 10=worst imaginable pain)—at least daily for the previous 2 months; and (3) willing to avoid both changes to their analgesic regimen as well as elective surgical procedures for 70 days after initiation of treatment with PEMF therapy.

Inclusion criteria (surgical patients): Adult patients of at least 18 years of age undergoing one of the surgical procedures listed below:

- a. non-mastectomy breast surgery with a single-injection paravertebral nerve block
- b. laparoscopic or open cholecystectomy
- c. laparoscopic sleeve gastrectomy
- d. percutaneous nephrolithotomy
- e. ventral hernia repair
- f. inguinal hernia repair
- g. knee or hip arthroplasty
- h. foot/ankle surgery with at least moderate pain anticipated
- i. shoulder acromioclavicular joint repair, labral repair, subacromial decompression, or Bankart repair (without rotator cuff repair)
- j. hand/forearm/elbow/shoulder surgery with at least moderate pain anticipated
- k. spinal surgery with at least moderate pain anticipated

Exclusion criteria: (1) concurrent use of an implanted pulse generator (e.g., cardiac pacemaker); (2) pregnancy; (3) incarceration. **Surgical participants only:** (4) chronic opioid/tramadol use (daily use within the 2 weeks prior to surgery and duration of use > 4 weeks); (5) neuro-muscular deficit of the surgical area/limb; (6) a planned postoperative perineural local anesthetic infusion.

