12. INFORMED CONSENT

Amputees. Individuals interested in the study will contact a research coordinator or investigator by email or telephone (contact information provided in the IRB-approved advertisements). Patients meeting inclusion and exclusion criteria will be presented with the study and provided the IRB-approved ICF and HIPAA consent electronically for their review. Individuals wishing to participate will have the option to (1) print the IRB-approved consent forms, sign the forms, and return them via the U.S. Postal Service; or (2) have UCSD send them the consent forms via the U.S. Postal Service, of which they may then sign and return in pre-addressed and stamped envelopes provided in the original envelope. Following receipt of the signed consent forms, participants will be randomized and sent an active or sham PEMF device by U.S. Postal Service with instructions to contact the investigative team upon arrival for assistance in applying the device.

Surgical participants. Candidates who meet inclusion and exclusion criteria and desire study enrollment will be scheduled to arrive the day of surgery 15 minutes earlier than normal to allow for written informed consent and baseline information collection. Written informed consent will be attained prior to any measurements or procedures prior to surgery. When participants present for surgery, research coordinators will provide and attain written informed consent. This will occur in private patient care areas, so that participants may feel comfortable asking questions of the research coordinator.

We do not foresee any issues relevant to the mental capacity of the potential human participants. Written, informed consent will be attained prior to any study procedures or measurements; and participants will not receive procedure-related sedation until following the written, informed consent process is completed. Participants will be provided privacy and time for decision making both in the study description/explanation telephone call to an investigator or research coordinator, as described above; and, the morning of the initial treatment using a private patient care area to again review the study, informed consent form, and answer any remaining questions. As noted previously, participants may speak with an investigator by telephone from initial contact through the morning of treatment; and will have access during and following the treatment(s) with cellular phone and pager numbers provided upon discharge.

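### Surgical participants have no scheduled preoperative BPI, opioid, sleep or flexion measure, which gives up precision and a check on chance imbalance for almost no saving

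*Combined protocol and SAP*

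**What the plan says.** The Section 9 table is captioned "Summary of post-enrollment assessments". Its surgical half, "Surgical Patients Postoperative Days", covers Days 1, 2, 3, 7, 14, 21, 28 and 180. Opioid use and sleep are marked from Day 1, the BPI short form from Day 7, and passive flexion (knees and hips) on Day 14 only. Pain and opioid use are marked again at Day 180. The other half, "Amputees Post-Application Days", opens with a Day 0 column that carries opioid use, average and worst pain, BPI and sleep.

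The Procedures paragraph of Section 9 supplies the only itemised baseline: "we will record baseline anthropometric information (age, sex, height, weight, amputation details and current pain levels". Section 12 asks surgical participants to arrive "15 minutes earlier than normal to allow for written informed consent and baseline information collection" but does not say what that baseline contains.

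Section 10 excludes surgical patients with "chronic opioid/tramadol use (daily use within the 2 weeks prior to surgery and duration of use > 4 weeks". On allocation, Section 9 states: "Randomization will be stratified by surgical procedure/amputation, in block sizes of 2". The comparisons named at the end of Section 9 are unadjusted two-sample tests (t or Mann-Whitney, with chi-square or Fisher's exact for proportions). No baseline covariate is mentioned.

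**The concern.** Eligible surgery runs from cholecystectomy and hernia repair to knee and hip arthroplasty and spinal procedures. It is reasonable to expect starting pain and function to differ among people having the same operation, and perhaps most among arthroplasty patients. That is a clinical inference; the documents give no preoperative data.

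Three things are lost without a preoperative value:

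- **Precision.** A baseline that predicts the outcome removes part of the residual variance when it is used as a covariate.
- **A check on chance imbalance.** Stratification balances the type of operation, not patients' starting status within it. Phase II plans 30 cholecystectomy and 40 hip or knee participants, few enough for a chance imbalance to be plausible, and on these measures it could be neither seen nor adjusted for.
- **Interpretation of late values.** Pain or opioid use at Day 180 cannot be classed as new or pre-existing. A single Day 14 flexion value has the same weakness.

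**Working it through.** **Step 1: which surgical measures have a baseline?** The table is limited to assessments after enrollment, so its missing column does not settle the matter. The other places where a baseline could be specified are:

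- BPI, sleep and flexion: not in the surgical columns before Day 7, Day 1 and Day 14 respectively, not in the Section 9 baseline list, and not named in Section 12.
- Opioid use: not recorded as a baseline. Section 10 removes long-term daily users, so the gap is confined to shorter or intermittent use.
- Pain: current pain is in the baseline list, directly after amputation details. Whether it is meant for surgical participants is unclear, and it is a single current rating rather than the average and worst scores that form the outcome.

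**Step 2: what could a baseline be worth?** Only the Phase II summed pain score has the inputs needed. From the sample-size text of Section 9: sham mean 23.9, SD 12.3, reduction 33%, two-sided alpha 0.05, 70 participants allocated 1:1, so 35 per group. (Elsewhere, Sections 7 and 9 refer to 80 Phase II subjects; 70 is used here because it belongs to the calculation.)

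Difference = 0.33 × 23.9 = 7.887, or 7.89.

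The plan's own figure first: n per group = 2 × (1.960 + 0.842)² × 12.3² / 7.887² = 38.2, rounded up to 39. The plan states about 25, which these inputs do not reproduce. That is a separate matter and this point does not depend on it.

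Power at 35 per group (normal approximation), with the SD multiplied by √(1 − r²) when a baseline with correlation r is a covariate:

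- Unadjusted: standard error = 12.3 × √(2/35) = 2.940; 7.887/2.940 = 2.682; power = Φ(2.682 − 1.960) = 76.5%.
- r = 0.3: SD = 12.3 × √0.91 = 11.73; standard error 2.805; ratio 2.812; power = Φ(0.852) = 80.3%.
- r = 0.5: SD = 12.3 × √0.75 = 10.65; standard error 2.546; ratio 3.097; power = Φ(1.137) = 87.2%.

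The number per group for 80% power falls from 39 to 35 and 29 in the same three cases. The documents give no correlation, so r = 0.3 and 0.5 are assumptions that show a range. Any further gain from adjusting for procedure is not counted.

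**Step 3: the other measures.** The documents give no mean, SD or correlation for BPI, opioid use, sleep or flexion, so no figure can be computed for them.

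**The case against.** The strongest reply is that little is at stake. The Phase II primary outcome is a postoperative sum, not a change score. BPI interference, sleep and flexion are not outcomes of primary interest, and secondary results are to be read only as suggestive. Prior opioid use has to be ascertained anyway to apply the exclusion. Section 12 does schedule baseline collection and may cover more than it lists. Finally, a new column gains no precision while the tests remain unadjusted. All of this stands. It makes the point a cheap improvement rather than a defect that threatens the trial, and it means the analysis has to change along with the schedule.

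A reader might infer four stronger things that the documents do not support:

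- *That treatment effects cannot be separated from preoperative status.* Allocation is randomized 1:1 within procedure, so the between-arm comparison of postoperative values is unbiased.
- *That Aim 2 fails because it asks which patients respond.* Section 6 links patient characteristics to amputees, who have a Day 0 assessment. For surgical participants it asks about procedures, which are known and are the stratification factor.
- *That the missing baselines are lost for good.* Flexion may be in the chart for some knee and hip patients, although the documents do not say that it is.
- *That surgical pain has no baseline at all.* Current pain is listed; only its scope and its match to the outcome are in doubt.

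**Conclusion.** The gap holds for four surgical measures: BPI, opioid use, sleep and passive flexion. For opioid use it is small, because long-term daily users are excluded. For pain the problem is an unclear and imperfectly matched baseline, not an absent one. The consequence is lost precision, no check of imbalance within procedure, and late outcomes that cannot be set against a starting level; it is not bias. For the summed pain score the possible gain is roughly 4 to 11 percentage points of power at 35 per group. That range rests on the assumed correlations of 0.3 to 0.5, on the planned difference and SD, and on an analysis that uses the baseline. It should not be carried over to the other four measures.

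**What to change.** For surgical participants not yet enrolled:

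1. Add a preoperative column to the Section 9 table: BPI short form, recent opioid use, and sleep disturbances the previous night. Section 9 notes that average and worst pain are already within the BPI, so separate pain questions are not needed. Collect these in the time Section 12 reserves "to allow for written informed consent and baseline information collection".
2. For knee and hip patients, abstract preoperative passive flexion from the chart where it is recorded.
3. State in the Procedures paragraph whether current pain is recorded for surgical participants.
4. Replace the unadjusted comparison with one adjusted for the matching baseline value and the procedure stratum, specified before unmasking. For pain outcomes in those already enrolled, use current pain as the covariate where it is available.

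The cost is a few more minutes of contact before surgery, one chart abstraction for knee and hip patients, and some missing flexion values. No new visit is needed. The data would also supply the baseline-outcome correlations that are now unknown, which would help size the later trials this pilot is meant to inform.

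### Amputee pain change to Day 28: no baseline adjustment is specified, although the Day 0 score it needs is already collected

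*Combined protocol and SAP*

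**What the plan says.** All of this is in section 9 of the protocol (Research Design and Methods) unless noted.

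- **Outcome.** Under Primary end points, the first amputee outcome of primary interest is the change in average "residual and phantom limb pain scores between baseline and Day 28 of the initial treatment". The second is the Patient Global Impression of Change, which has no baseline and is not at issue here.
- **Status of the analysis.** The same paragraph calls the trial an exploratory pilot and adds "we therefore have no data analysis plan".
- **Tests named.** The closing statistical paragraph offers "Student's t-test for parametric continuous variables or Mann-Whitney U test for nonparametric or categorical variables", plus chi-square and Fisher tests for proportions. No covariate, regression or ANCOVA appears anywhere.
- **Data available.** The assessment table marks average NRS pain for amputees on Day 0 and on Day 28. The text says phantom and residual pain are scored separately each time. The Procedures paragraph also records "age, sex, height, weight, amputation details and current pain levels" after consent.
- **Size.** No amputee sample size is given. Section 10 caps enrollment at "270 participants in total", counting everyone who signs consent. Phase I has 150 surgical participants; Phase II has 80 or 70, depending on the paragraph.

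**The concern.** Specific Aim 2 (section 6) is to estimate the treatment effect so that later trials can be sized. For post-amputation pain, the amputee cohort is the only source of that estimate, and it is small.

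If the change is compared by a two-sample test, the baseline slope is in effect fixed at 1. When the true slope is below 1, this over-corrects chance baseline differences and adds baseline noise to the comparison. The interval is then wider than the same data allow, and the estimate is shifted whenever the arms happen to differ on Day 0. Randomization is stratified by procedure or amputation, not by baseline pain, so such differences are not designed out.

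The covariate that would deal with both problems is already on the schedule, but nothing says it will be used.

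**Working it through.** **No plan figure to reproduce.** The only sample size calculation in the protocol concerns the Phase II surgical summed pain score. It supplies no N, SD or correlation for amputees, so it is not an input.

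**Amputee number, by subtraction.** 270 − 150 − 80 = 40, or 270 − 150 − 70 = 50. At 1:1 allocation that is 20 to 25 per arm. This is an upper bound and assumes that the surgical phases fill.

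**Variance.** Let s be the Day 28 SD, k the baseline SD divided by the Day 28 SD, and r the baseline-to-Day 28 correlation. All three are assumptions. Per participant:

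- raw change: s²(1 + k² − 2rk)
- ANCOVA, large sample: s²(1 − r²)
- ratio: (1 − r²)/(1 + k² − 2rk), which is (1 + r)/2 when k = 1

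The change-score term exceeds the ANCOVA term by s²(k − r)². So the large-sample ratio is never above 1, and it equals 1 only when r = k, that is, when the slope r/k is exactly 1.

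**Small-sample cost.** Estimating the slope inflates the ANCOVA variance by 1 + 1/(N − 4): 1.028 at N = 40 and 1.022 at N = 50. The t quantile uses N − 3 instead of N − 2 degrees of freedom.

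**Equal SDs (k = 1):**

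| r | Large-sample ratio | With inflation, N = 40 | CI half-width ratio, N = 40 |
|---|---|---|---|
| 0.3 | 0.65 | 0.668 | 0.82 |
| 0.5 | 0.75 | 0.771 | 0.88 |
| 0.7 | 0.85 | 0.874 | 0.94 |
| 0.8 | 0.90 | 0.925 | 0.96 |
| 0.9 | 0.95 | 0.976 | 0.99 |

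Break-even is at r of about 0.94 (N = 40) or 0.955 (N = 50). A simulation of 6,000 trials of 40 people, with scores rounded and bounded at 0 and 10, gave variance ratios of 0.67, 0.76 and 0.86 at r = 0.3, 0.5 and 0.7.

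**Unequal SDs:**

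- k = 0.8, r = 0.5: 0.75/0.84 = 0.89
- k = 0.8, r = 0.7: 0.51/0.52 = 0.98; with inflation, 0.981 × 1.028 = 1.008 at N = 40, so essentially no gain
- k = 0.8, r = 0.8: 0.36/0.36 = 1.00
- k = 1.25, r = 0.5: 0.75/1.3125 = 0.57

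**In NRS points (k = 1, r = 0.5).** Half-width is t × s × √(variance factor) × √(4/N). With an assumed SD of 2.5 and N = 40:

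- change: t(38) × 2.5 × √1.00 × √0.1 = 1.60
- ANCOVA: t(37) × 2.5 × √(0.75 × 1.028) × √0.1 = 1.41

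At N = 50 the pair is 1.42 and 1.25. At SD 2 and N = 40 it is 1.28 and 1.13; at SD 1.5, 0.96 and 0.84.

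**Chance imbalance.** With a baseline SD of 2.5 and 20 per arm, the standard error of the baseline difference is 2.5 × √(2/20) = 0.79. A gap of 1 point or more in either direction then occurs about 21% of the time for a given pain type (about 16% with 25 per arm). A 1-point gap shifts the change-score contrast by 1 − r/k in favor of the arm with the higher baseline when the slope is below 1. The shift is 0.5 points at k = 1, r = 0.5; 0.3 at k = 1, r = 0.7; and 0.125 at k = 0.8, r = 0.7.

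**The case against.** **The unadjusted analysis is not actually stated.** A reader might infer that the protocol chose an inferior method. The documents do not support that. The protocol disclaims an analysis plan, and naming a change as the outcome does not fix the estimator: ANCOVA on the change gives the same treatment estimate as ANCOVA on the Day 28 score. The list of tests also follows the Phase II surgical text, so whether it governs amputees is unclear. This objection stands, and the point is therefore a gap in specification.

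**The size of the gain is assumed.** A reader might take 25% less variance as established, or suppose that baseline pain will vary widely because entry needs only NRS 3. Neither follows. The protocol gives no amputee SD or correlation, and the entry threshold could instead narrow the baseline spread and leave almost no gain. Because entry is on residual and/or phantom pain, a participant may qualify on one type and score low on the other, so the direction is not settled. The figures above also compare only with the t-test, not with Mann-Whitney.

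**The change score is not biased by design.** Correct: under randomization it is unbiased on average. The shift is conditional on the baseline gap that happens to occur.

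**Amputees cross over at Day 35.** The second period may also inform Aim 2, but this outcome is limited to the initial treatment, so the comparison is between parallel arms.

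**Conclusion.** The concern holds as a gap: baseline adjustment is not provided for, and the scheduled data would support it. With equal SDs, ANCOVA removes 10% to 35% of the large-sample variance for r from 0.8 down to 0.3. If the baseline spread is narrower than the Day 28 spread, the gain can be negligible. At 40-50 amputees, the lost degree of freedom and the estimated slope cost about 2-3% of variance, which outweighs the gain only when the slope is close to 1. The adjustment is therefore cheap but not strictly free. In return it removes the shift from chance baseline imbalance, given a roughly linear relation.

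The results rest on assumed r and SDs and on an amputee number obtained by subtraction. Severity is modest: this is an exploratory pilot, with no powered amputee test and no stated amputee sample size.

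**What to change.** Add a short statement to section 9, under Primary end points and in the statistical paragraph:

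- For residual and phantom pain separately, compare the Day 28 average NRS of the initial treatment (or the change, which gives the same treatment estimate) between arms by ANCOVA, with that pain type's own Day 0 average NRS as covariate.
- Report the adjusted difference with its 95% CI. The raw change can still be reported descriptively.
- Define baseline as the Day 0 score taken before device activation. The table lists Day 0 among the post-application days, and pain is also recorded after consent, so the wording should say which score counts.
- State who enters each model, since some participants may have little or no pain of one type at baseline.

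The cost is a few lines of text and one degree of freedom per model. No new data are needed.
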